# 1.0 Abbreviations and Definitions

| AE      | adverse event                             |
|---------|---|
| ALK-P   | alkaline phosphatase                      |
| ALT     | alanine aminotransferase                  |
| ANCOVA  | analysis of covariance                    |
| ANOVA   | analysis of variance                      |
| AST     | aspartate transaminase                    |
| AUDIT   | alcohol use disorders identification test |
| Bili    | Bilirubin                                 |
| CBC     | complete blood count                      |
| cm      | centimeter                                |
| ConMeds | concomitant medications                   |
| DHA     | docosahexaenoic acid                      |
| EE      | ethyl ester                               |
| EPA     | eicosapentaenoic acid                     |
| FFQ     | food frequency questionnaire              |
| FIB-4   | fibrosis score                            |
| HOMO-IR | homeostatic model of insulin resistance   |
| IIT     | intent-to-treat                           |
| kg      | kilogram                                  |
| MRI     | magnetic resonance imaging                |
| PBMC    | peripheral blood mononuclear cells        |
| РВО     | Placebo                                   |
| PDFF    | proton density fat fraction               |
| PP      | per protocol                              |
| NAFLD   | non-alcoholic fatty liver disease         |
| SAE     | serious adverse event                     |
| TEAE    | treatment emergent adverse event          |
|         |   |

# 2.0 Introduction

This study is designed to evaluate the combination of vitamin E acetate and docosahexaenoic acid ethyl ester (DHA EE) against placebo to demonstrate efficacy and safety. Each active product is also included as an additional treatment arm to gain further insight into its contribution to changes in NAFLD parameters and to collect additional safety data. For the remainder of this document:

- PBO refers to the placebo treatment arm
- vitamin E refers to the vitamin E acetate alone treatment arm
- DHA EE + vitamin E refers to the combination treatment arm
- DHA EE refers to the DHA alone treatment arm

# 3.0 Study Objectives and Endpoints

## 3.1 Primary Objective

To determine the efficacy of the combination of vitamin E and omega-3 fatty acid (DHA EE + vitamin E) versus placebo (PBO) on reducing liver fat content after 6 months of intervention in adults with NAFLD. The efficacy of the treatment will be assessed by a decrease in hepatic fat fraction (%) relative to baseline measured by MRI-PDFF after 6 months of intervention.

## 3.2 Secondary Objective(s)

- To determine effect of vitamin E versus PBO on reducing liver fat after 6 months of intervention in adults with NAFLD.
- To determine effect of DHA EE versus PBO on reducing liver fat after 6 months of intervention in adults with NAFLD.
- To determine the change after 6 months of DHA EE and /or vitamin E intervention in anthropometric, metabolic, hepatologic, nutrient, and inflammatory parameters, and quality of life status of adults with NAFLD.

# 3.3 Safety Objective(s)

To examine any treatment-emergent adverse event (TEAEs) and changes in clinical safety laboratory parameters. Safety will be assessed with vital signs, serum hematology and biochemistry, and AE/SAE reporting.

## 4.0 Definition of Endpoint Measures

## 4.1 Primary Endpoint

The primary objective will be assessed by the hepatic fat fraction [%], as measured by MRI-PDFF, after 6 months of intervention of vitamin E + DHA combination compared to the placebo adjusted for baseline.

#### 4.3 Exploratory Endpoint(s)

- The difference after 6 months of intervention between specified treatment groups (vitamin E + DHA combination vs. placebo, vitamin E vs. placebo, DHA vs. placebo) on the hepatic fat fraction [%], adjusted for baseline, stratified by the following single nucleotide polymorphisms (SNPs):
  - PNPLA3 genotype (CC versus CG + GG)
  - HSD17b genotype (GA + GG versus AA)
  - Haptoglobin genotype (\*2/\*2 versus \*1/\*2 + \*1/\*1)
- The difference after 6 months of intervention between specified treatment groups (vitamin E + DHA combination vs. placebo, vitamin E vs. placebo, DHA vs. placebo) on the hepatic fat fraction [%], adjusted for baseline, stratified by the following demographic and baseline variables:
  - Type II diabetes (yes/no)
  - Sex (male/female)
  - Baseline FIB-4 score (low risk [<1.3] versus indeterminate/high risk [≥1.3])

  - BMI (<30 kg/m^2 [underweight/healthy] versus  $\geq$ 30 kg/m^2 [overweight/obese])
  - Age (cutoff defined by the median of the baseline distribution)
  - ALT level at baseline (cutoff defined by the median of the baseline distribution)
- Transcriptome analysis will be performed using the gene expression data of peripheral blood mononuclear cells in a subset of approximately 40 subjects that complete the intervention. Changes in gene expression from baseline to end of treatment will be examined.
- The difference after 6 months of intervention between specified treatment groups (vitamin E + DHA combination vs. placebo, vitamin E vs. placebo, DHA vs. placebo) on the LC-PUFA derived oxylipins

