9.3.6 Compliance Analysis

A compliance analysis will be performed on all randomized participants who completed the study (6 mos) and ingested at least 80% of the study product using plasma DHA levels (μ g/ml) and plasma α -tocopheryl (μ mol/L) to confirm accuracy of the pill counts. ANOVA models will be employed with treatment as a factor. Frequency counts and percentages will also be presented for subjects who were at least 80% compliant by treatment group. Differences in this categorical outcome will be assessed using Fisher's Exact Test.

9.3.7 Sample size:

Le et al.[1] report that the variability (standard deviation) of the within-subject change in liver fat [%] for a period of 24 months in a similar population and with the same measurement method (MRI-PDFF) is 7%. Expecting a within-subject 3.64% absolute reduction in liver fat for the combination group vs. placebo [1, 2] and setting α =0.05 and 80% power, n=60/arm for the combination and placebo groups are needed (G*power 3.1.9.2, two-sample t-test).

To estimate the secondary endpoints (effect vs. placebo of the components (DHA EE alone and Vitamin E alone)) with a given precision (confidence interval width) of $\pm 3\%$ of liver fat, we need n=30/arm for the DHA EE only and Vitamin E only groups, leading to a necessary sample size of 180. With 10% expected attrition, the total sample size is 200 subjects.

Subjects will be stratified by Type II Diabetes diagnosis (no greater than 50% of sample). Subjects who withdraw prematurely from the study will not be replaced.

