# 7.0 Determination of Sample Size and Randomization

As indicated in section 9.3.7 of the study protocol, with 60 subjects per arm for the combination (DHA EE + vitamin E) and PBO groups, there is 80% power to detect a 3.64% absolute reduction in liver fat assuming a standard deviation of 7% and a two-sided 0.05 significance level with a two-sample t-test (G\*power 3.1.9.2). To estimate the secondary endpoints of the PBO compared to the components (DHA EE, vitamin E) with a given precision of ±3% of liver fat, a total of 30 subjects per arm are needed for the

DHA EE and the vitamin E groups. Accounting for an expected 10% attrition, the resulting required sample size was 200 subjects.

Subjects will be randomly assigned to one of four treatment arms following an unequal allocation of 65/65/35/35 for combination (DHA EE + vitamin E), PBO, DHA EE, and vitamin E, respectively. A computer generated randomization scheme (i.e. interactive web based response system [IWRS]) will be used to assignment stratified by Type II diabetes.

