# 8.4 Exploratory Endpoint Analyses

The interaction between intervention groups and each of PNPLA3, HSD17b, and haptoglobin SNPs, as well as with the specified categorical demographic and baseline variables (section 4.3), on the 6-month hepatic fat fraction will be evaluated with the model specified in the primary endpoint analysis (section 8.2) where the interaction between intervention group and respective variable (i.e. SNP, categorical variable) will also be included. A separate model for each will be constructed for each exploratory interaction. Pairwise comparisons of DHA EE + vitamin E vs. PBO, vitamin E vs. PBO, and DHA EE vs. PBO will be estimated for each genotype / category along with 95% confidence intervals and presented in forest plots.

Transcriptomics (Tx) analysis of the PBMC gene expression will follow a discovery approach. The analyses will be performed internally at DSM. In brief, the gene expression workflow will be performed as defined by the Partek Software (https://www.partek.com/). The large data set will be first visually explored using different techniques like heat maps, clustering and principal component analysis (predefined by the Tx software application). This will also trigger the thresholds to be used in further processing. ANOVA pairwise group comparisons (placebo vs the different treatments) will be applied with the goal to identify genes that are significantly differently expressed. The contrast method of Fisher's least significant difference (LSD) will be used (Gene expression workflow, Partek Software) and q-Values (FDR) will be calculated to correct for multiple testing. The q-values will be set after inspection of the whole Tx data set, but will be between q = 0.05 - 0.15, if possible. The filtering will use the change fold of +1.2 fold up- and -1.2 fold down regulation versus the placebo group with the lowest p-values

2017-1088 (PUVENAFLD) SAP Version 4.0

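### SAP 4.3 and 8.4 examine age, ALT, FIB-4 and BMI as effect modifiers only after cutting each in two; a continuous interaction would use more of the collected information at almost no cost

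*SAP*

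**What the plan says.** SAP 4.3 lists the baseline variables by which the 6-month liver fat comparison will be examined. Four of them are numeric and each is reduced to two groups:

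- Age: "Age (cutoff defined by the median of the baseline distribution".
- ALT: "ALT level at baseline (cutoff defined by the median of the baseline distribution".
- FIB-4: below 1.3 against 1.3 or more, labelled as risk categories.
- BMI: below 30 against 30 kg/m² or more, labelled as weight categories with two cited sources.

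SAP 8.4 evaluates the interaction of treatment with the genotypes, "as well as with the specified categorical demographic and baseline variables (section 4.3". It adds each interaction to the primary model in a separate fit. It then reports each active arm against placebo within each category, with 95% confidence intervals, in forest plots. Neither section plans a continuous interaction term, a spline or a sensitivity version. All of this is labelled exploratory, and the documents claim no power for it.

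**The concern.** All four variables are collected or computed as numbers. Eligible ALT runs from 40 to just under 250 U/L (Protocol 4.2.1 and 4.2.2), about a sixfold range that becomes low or high. A two-group version treats a subject just above the cut like one far above it. The primary model already carries baseline liver fat as a continuous covariate (SAP 8.2), so a continuous modifier would fit the plan's own framework.

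For age and ALT there is a second difficulty. The rule for the cut is fixed in advance, but its value is unknown until the data are in and will differ in another trial, so the two-group result is hard to carry over.

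What is at stake is the precision of interaction estimates that are already imprecise in a trial sized for a main effect.

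**Working it through.** **Inputs from the documents.** SAP 7.0 states that "there is 80% power to detect a 3.64% absolute reduction in liver fat" with 60 subjects in each of the combination and placebo arms, "assuming a standard deviation of 7% and a two-sided 0.05 significance level". Allocation is 65/65/35/35 with 10% attrition.

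**Inputs not in the documents, assumed here.** These are the shape of each modifier's distribution, the shares above FIB-4 1.3 and BMI 30, and the form of any effect modification. I take normal or log-normal modifiers, linear modification, and splits from 50/50 to 90/10.

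**Step 1: the plan's own figure.** n per arm = 2 × (1.96 + 0.842)² × 7² / 3.64² = 58.1, rounded up to 59 by the normal approximation. Exact t-test power is 79.98% at 59 and 80.6% at 60, so 60 per arm is right. The total also reproduces: 180 / 0.90 = 200.

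**Step 2: information kept by a split.** For a normal modifier with linear modification, cut so that a share p lies on one side, the information kept is φ(z_p)² / [p(1 − p)].

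| Split | Information kept | Lost |
|---|---|---|
| 50/50 | 0.159 / 0.25 = 0.637 | 36% |
| 70/30 | 0.576 | 42% |
| 75/25 | 0.539 | 46% |
| 80/20 | 0.490 | 51% |
| 90/10 | 0.342 | 66% |

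Variable by variable, under assumed distributions:

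- ALT, log-normal and limited to the eligible range, median split: 34–35% lost on the log scale, 48–50% on the raw scale.
- FIB-4, median 0.9–1.3 and log-SD 0.5: 36–48% lost on the log scale.
- BMI, mean 33–36 and SD 5–6: 44–56% lost. The top of that range has 84% of subjects above the cut, beyond an 80/20 split.

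**Step 3: power for a large interaction, 60 against 60, SD 7.** The standard error of a slope difference per SD of the modifier is 7 × √(2/60) = 1.278. For 80% power the slope difference must be 2.80 × 1.278 = 3.58 points per SD. The two median halves lie 2√(2/π) = 1.596 SD apart on average, so this is a gap of 3.58 × 1.596 = 5.7 points in treatment effect between halves, about 1.6 times 3.64. With a split, power = Φ(2.80 × √(information kept) − 1.96):

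- median: Φ(2.235 − 1.96) = 61%
- 70/30: 57%
- 80/20: 50%
- 90/10: 37%

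Two-arm simulation (4,000 runs, slope 3.64 points per SD) gave 78% continuous against 59% at the median, and 79% against 46% at 80/20. A four-arm simulation with 58/58/31/31 subjects and a slope of 0.53 SD per SD (0.53 × 7 × 1.596 = 5.9 points between halves, again about 1.6 times the design effect) gave 79% continuous, 60–62% at the median and 51–52% at 75/25.

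**Step 4: power for a gap equal to the design effect.** For 3.64 points between median halves:

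- Split: standard error 7 × √(4/30) = 2.556; 3.64 / 2.556 = 1.424; power about 30%.
- Continuous: slope 3.64 / 1.596 = 2.281; 2.281 / 1.278 = 1.785; power about 43%.

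Simulation gave 28% and 42%. With a median split, the gap detectable with 80% power is 2.80 × 2.556 = 7.2 points, about twice the design effect. For a single agent against placebo (30 against 60) it is 8.8 points.

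**The case against.** - **These analyses are exploratory.** No power is claimed and no decision is tied to them. The planned output is estimates with intervals by category, a readable display. This stands and limits the weight of the point. It does not argue against using the data better.
- **The advantage of a continuous term is conditional.** If modification is a step at the cut, splitting loses nothing and the linear term becomes the less efficient choice. At a median step it keeps 2/π = 64% of the information, so the 80% and 61% in the working change places. This stands as the named downside. A step exactly at the sample median of age or ALT has no rationale in the documents. For FIB-4 and BMI, whose cuts are fixed and carry category labels, a step is less implausible.
- **The median cuts are pre-specified and use baseline data only.** They cannot be tuned to the outcome, and nothing here suggests otherwise. The objection about carrying over to another trial applies to age and ALT alone.
- **The change would not make these analyses well powered.** That is true: about 43% for a 3.64-point gap is still low.

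Two stronger readings are tempting. A reader might infer that power drops by a third to a half because information does. It does not: 80% to 61% is a relative loss of 24%, and 80% to 50% is 38%. A reader might also infer that the four-arm by two-level term commits the trial to a joint test on 3 degrees of freedom. SAP 8.4 names no such test, and it already reports combination against placebo within each category.

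**Conclusion.** The point holds as a cheap improvement to an exploratory analysis. With normal (or log-normal) modifiers and linear modification, the median cuts of age and ALT discard about 36% of the information on the interaction. The fixed cuts of FIB-4 and BMI discard about 36–51% if the split lies between 50/50 and 80/20, and about two thirds at 90/10; the documents do not say where these splits fall.

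In power, the cost is about 19 points at a median split and 30 at 80/20 for a large interaction, and about 13 points (43% to 30%) for a gap equal to the design effect. The powers use the planning SD of 7. A smaller residual SD after baseline adjustment would raise them but leave the information ratios unchanged.

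The case is firm for age and ALT and weaker for FIB-4 and BMI. The documents do not support any inference that the primary comparison is impaired: SAP 8.2 does not use these categories.

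**What to change.** In SAP 8.4, for age, log ALT, log FIB-4 and BMI:

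1. Add the modifier as a continuous covariate, with its interaction with treatment arm, to the primary model, one model per modifier. Name this as the main interaction analysis.
2. Report the combination-versus-placebo interaction contrast with its 95% confidence interval, and the same contrast for each single agent.
3. Keep the two-group estimates of SAP 4.3 for the forest plots.

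The cost is a few lines of SAP text and four extra models, with no new data, visits or subjects. The downside is the assumed linear or log-linear form. The retained category display lets a reader look for a step, and a spline with few degrees of freedom could be added as a check. If the SAP can no longer be changed, the continuous analysis can be reported as a described and justified deviation under SAP 9.0.

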#### 4.4 Post hoc analysis

From the additional blood samples collected at Visit 1 and Visit 4, in the event of a positive treatment effect as defined by the primary endpoint, the following biomarkers will be analyzed:

- ELF (enhanced liver fibrosis)
- Pro-C3

## 5.0 Trial Design and Visit Structure

This is a multi-center, randomized, double-blind, placebo-controlled, parallel 4-arm intervention superiority trial in adults with NAFLD. Subjects are randomized to one of four treatment arms (vitamin E alone, DHA alone, vitamin E + DHA, or placebo) stratified by Type II Diabetes diagnosis.

The total study duration per subject is 6 months with 6 subject contact points including 2 screening visits, randomization/baseline visit, a one-month phone call, a 3-month visit, and a 6-month visit. The following schedule of assessments is from section 6.2 of the study protocol.

| Visits  | V0
Screening + | 2 nd Screening
V1 + | V2 Randomization | Phone call at 1
mos  | V3 3mos     | V4 6mos      |
|---|------------------------------|--|------------------|-------------------------------------|-------------|--------------|
| Day**   | -28 to -14                   | -21 to -5                                    |                  | 30±3                                | 90 -7 to +3 | 180 -7 to +3 |
| Informed Consent  | х                            |  |                  |                                     |             |              |
| Medical History   | х                            |  |                  |                                     |             |              |
| Physical Examination  | х                            |  |                  |                                     | х           |              |
| Liver Fibroscan   | Х                            |  |                  |                                     |             |              |
| MRI-PDFF for Liver fat  |                              | Х  |                  |                                     |             | х            |
| Clinical chemistry*   | х                            | ALK-P, AST,
ALT, Bili only                |                  |                                     | х           | x            |
| HbA1c and Insulin   | Х                            |  |                  |                                     |             | х            |
| Hep A (HAVIgM) #                                       | х                            |  |                  |                                     |             |              |
| Hematology*   | Х                            |  |                  |                                     | CBC         | х            |
| Coagulation: INR  | х                            |  |                  |                                     |             |              |
| Urine pregnancy test  | Х                            |  | Х                |                                     |             |              |
| Skinner questionnaire                                 | Х                            |  |                  |                                     |             |              |
| AUDIT questionnaire^  | Х                            |  |                  | х                                   | Х           | Х            |
| Vital signs   | Х                            |  | Х                |                                     | Х           | Х            |
| Lipid panel* including
oxidized LDL                            |                              | х  |                  |                                     |             | х            |
| Plasma/serum for
inflammatory markers                          |                              | х  |                  |                                     |             | x            |
| Anthropometrics   | х                            |  |                  |                                     | х           | х            |
| Randomization   |                              |  | Х                |                                     |             |              |
| DHA & α-tocopheryl
determination and
oxylipins  |                              | x  |                  |                                     | х           | x            |
| Product dispense  |                              |  | х                |                                     |             |              |

#### Table 1: Schedule of assessments

2017-1088 (PUVENAFLD) SAP Version 4.0

| Compliance-Pill count      |   |   |   | Х | Х | Х |
|----------------------------|---|---|---|---|---|---|
| Adverse event
reporting |   |   | Х | Х | х | Х |
| ConMeds                    |   |   | х | х | Х | Х |
| FFQ                        | Х |   | х | х | Х | Х |
| SF-36 questionnaire        |   |   | х |   |   | Х |
| Biosample collection ¶     |   | Х |   |   |   | Х |

\* fasted blood draw required and ALT, AST, Alk-P, bilirubin is measured 2x

\*values obtained at screening (except vital signs and FFQ) will be considered 'baseline' values

#HAVIgM to be performed unless negative results in past 3 years

oxylipins measured only at V1 and V4.

Skinner Lifetime Drinking Questionnaire and AUDIT given at V0 Screening

 Reminder phone calls at months 2,4 and 5 are advised to assist with retention and check on subject compliance, no diet fluctuations, ConMeds, and AEs.

\*\* Additional time may be allowed between study visits with approval and subsequent protocol deviation.

^ Audit questionnaire - Self-report version is collected at V0, V3 and V4 and the interview is only conducted during the 1-month phone call

¶ Refer to lab manual for sample collection table - Exploratory analyses include gene expression at V1 and V4 in a subset of 40 subjects, and PNPLA3, HSD17b, haptoglobin genotyping at V1.

